10.6 Measures to Minimize Bias

10.6.1 Enrollment/Randomization/Masking Procedures

While blinding would be desired in this study, it is not feasible due to the study drugs having different formulations. Therefore, once randomization is performed, investigators and patients will know which study arm patients are assigned to. The implication of lack of blinding is that there could be potential bias regarding patient report of symptomatic improvement and provider record of measurements, such as VAS scores. However, the goal of this study is to be a pilot study to allow for a larger RCT in the future that could potentially be blinded and allow for minimization of biases.

To reduce bias, randomization will be used with allocation 1:1 to each treatment group. Block randomization will be used due to the small sample size of each study arm using Trialmaster. Replacement of patients who discontinue will not be allowed since the enrollment goal of 60 is conservative to account for drop-outs, early discontinuation, and lost to follow up patients.

11 Source Documents and Access to Source Data/Documents

Source data is all information, original records of clinical findings, observations, or other activities in a clinical trial necessary for the reconstruction and evaluation of the trial. Source data are contained in source documents. Examples of these original documents, and data records include: hospital records, clinical and office charts, laboratory notes, memoranda, subjects'

CONFIDENTIAL

This material is the property of the NYU School of Medicine and Langone Medical Center. Do not disclose or use except as authorized in writing by the study sponsor
Interventional Template Version: 11 January 2019

diaries or evaluation checklists, pharmacy dispensing records, recorded data from automated instruments, copies or transcriptions certified after verification as being accurate and complete, microfiches, photographic negatives, microfilm or magnetic media, x-rays, subject files, and records kept at the pharmacy, at the laboratories, and at medico-technical departments involved in the clinical trial. It is acceptable to use CRFs as source documents. If this is the case, it should be stated in this section what data will be collected on CRFs and what data will be collected from other sources.

The study case report form (CRF) is the primary data collection instrument for the study. All data requested on the CRF must be recorded. All missing data must be explained. If a space on the CRF is left blank because the procedure was not done or the question was not asked, write "N/D". If the item is not applicable to the individual case, write "N/A". All entries should be printed legibly in black ink. If any entry error has been made, to correct such an error, draw a single straight line through the incorrect entry and enter the correct data above it. All such changes must be initialed and dated. DO NOT ERASE OR WHITE OUT ERRORS. For clarification of illegible or uncertain entries, print the clarification above the item, then initial and date it.

Access to study records will be limited to IRB-approved members of the study team. The investigator will permit study-related monitoring, audits, and inspections by the IRB/EC, the sponsor, government regulatory bodies, and University compliance and quality assurance groups of all study related documents (e.g. source documents, regulatory documents, data collection instruments, study data etc.). The investigator will ensure the capability for inspections of applicable study-related facilities (e.g. pharmacy, diagnostic laboratory, etc.).

Participation as an investigator in this study implies acceptance of potential inspection by government regulatory authorities and applicable University compliance and quality assurance offices.

12 Quality Assurance and Quality Control

QC procedures will be implemented beginning with the data entry system and data QC checks that will be run on the database will be generated. Any missing data or data anomalies will be communicated to the site(s) for clarification/resolution.

Following written SOPs, the monitors will verify that the clinical trial is conducted and data are generated, documented (recorded), and reported in compliance with the protocol, GCP, and the applicable regulatory requirements (e.g., Good Laboratory Practices (GLP), Good Manufacturing Practices (GMP)).

The investigational site will provide direct access to all trial related sites, source data/documents, and reports for the purpose of monitoring and auditing by the sponsor, and inspection by local and regulatory authorities.

CONFIDENTIAL

This material is the property of the NYU School of Medicine and Langone Medical Center. Do not disclose or use except as authorized in writing by the study sponsor
Interventional Template Version: 11 January 2019

13 Ethics/Protection of Human Subjects

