7.2.4 Final Study Visit

Final Study Visit (Visit 2, Week 12 +/- 3 to 5 days)

- Record AE as reported by participant or observed by investigator
- Record participant's adherence to treatment regimen
- Record VAS scores for dyspareunia, itching, and dryness
- Record vital signs, results of physical exam including pelvic
- Collect pelvic samples for vaginal pH and vaginal tissue scraping for VMI
- Have patient fill out VSQ, FSFI, VSI, PGI-I
- Discuss the preliminary changes in their symptoms, if any exist
- Provide contact information for [name] to communicate any AE or side-effect experienced after the end of the study if patient believes it is related to the study

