2 = Most times (more than half the time)
3 = Sometimes (about half the time)
4 = A few times (less than half the time)
5 = Almost never or never

18. Over the past 4 weeks, how **often** did you experience discomfort or pain following vaginal penetration?

0 = Did not attempt intercourse
1 = Almost always or always
2 = Most times (more than half the time)
3 = Sometimes (about half the time)
4 = A few times (less than half the time)
5 = Almost never or never

19. Over the past 4 weeks, how would you rate your **level** (degree) of discomfort or pain during or following vaginal penetration?

0 = Did not attempt intercourse
1 = Very high
2 = High
3 = Moderate
4 = Low
5 = Very low or none at all

CONFIDENTIAL

19h Vaginal Symptom Index

Vaginal Symptom Index Score

1. Vaginal dryness

0=none
1=mild
2=moderate
3=severe

2. Vaginal soreness

0=none
1=mild
2=moderate
3=severe

3. Vaginal irritation

0=none
1=mild
2=moderate
3=severe

4. Vaginal discharge

0=none
1=mild
2=moderate
3=severe

5. Dyspareunia

0=none
1=mild
2=moderate
3=severe

19i Patient Global Impression of Improvement

Check the number that best describes how your post-intervention condition is now, compared with how it was before the intervention:

Very much better = 1

Much better = 2

A little better = 3

No change = 4

A little worse = 5

Much worse = 6

Very much worse = 7

CONFIDENTIAL

This material is the property of the NYU School of Medicine and Langone Medical Center. Do not disclose or use except as authorized in writing by the study sponsor
Interventional Template Version: 11 January 2019

20 Schedule of Events

Activity	Visit 1 (Day 0)	Visit 2 (12 weeks +/- 1 week)
Study team procedures		
Routine history of present illness, medical, obstetrical, gynecological, surgical, medication, HRT usage history	X	
Vitals and routine physical exam including pelvic	X	X
GSM Diagnosis	X	
Consent	X	
VAS score for dyspareunia, itching, and dryness	X	X
Rugal fold presence	X	X
VSQ, FSI, VSI	X	X
Randomization	X	
Study drug/device dispensation	X	
Participant study drug/device compliance check		X
Check for side-effects and/or AE due to study agent		X
Laboratory Assessments		
Urine pregnancy test	X	
Urine analysis	X	
Vaginal pH	X	X
VMI	X	X

CONFIDENTIAL

This material is the property of the NYU School of Medicine and Langone Medical Center. Do not disclose or use except as authorized in writing by the study sponsor
Interventional Template Version: 11 January 2019

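### The protocol names provider recording of the VAS as a bias of open treatment and leaves it in place; it should state that participants mark the three scales themselves

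*Combined protocol and SAP*

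**What the plan says.** Section 10.6.1 explains that the two products differ in formulation, so blinding is not feasible and "once randomization is performed, investigators and patients will know which study arm patients are assigned to". It names two consequences in one sentence, one on the patient's side and one on the provider's: "there could be potential bias regarding patient report of symptomatic improvement and provider record of measurements, such as VAS scores". Its answer is that this is a pilot meant "to allow for a larger RCT in the future that could potentially be blinded". The only measure it offers for the present trial is allocation: "To reduce bias, randomization will be used with allocation 1:1 to each treatment group", in blocks.

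The week 12 list in 7.2.4 has "Record VAS scores for dyspareunia, itching, and dryness" as a staff action and, as a separate item, "Have patient fill out VSQ, FSFI, VSI, PGI-I". The baseline list in 7.2.3 makes the same split, with the VSQ, FSFI and VSI as the self-completed forms. In the 12-week branch of 7.2.5, recording the VAS shares a line with taking the symptom history, and only the VSQ is self-completed. Section 4.2.2 makes change in the three VAS scores a secondary endpoint, and 10.4.2 gives the scale as 0 to 10.

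**The concern.** Two people at the week 12 visit know the arm: the woman and the person who records her answer. Nothing in an open trial removes the first source of bias for a symptom scale. The second exists only if a provider mediates the answer, and the reason given in 10.6.1 (different formulations) does not explain why a provider should. The stated safeguard, blocked 1:1 randomization, balances the arms at entry and does nothing about how an outcome is recorded twelve weeks later.

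At stake are the VAS estimates. Section 10.1 will report treatment effects with 95% confidence intervals, and 2.1 and 10.2 intend the pilot to inform a larger trial. Section 10.2 expects HLA to improve on estrogen and names the VAS among the outcomes, so a recorder's expectation could have a direction, although 2.3 states a hypothesis of equality.

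**Working it through.** The plan gives no figure on this point and none is needed. The check is to set the places that mention the VAS side by side.

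| Place | VAS | Self-completed forms | Arm known? | VAS position in the list |
|---|---|---|---|---|
| 7.2.3 baseline | staff record | VSQ, FSFI, VSI | no, randomization is listed later | after the exam, GSM diagnosis and eligibility check |
| 7.2.4 week 12 | staff record | VSQ, FSFI, VSI, PGI-I | yes | before the exam and before discussion of change |
| 7.2.5, 12 weeks of use | staff record, with symptom history | VSQ | yes | before the exam and before discussion of change |
| 7.2.5, under 12 weeks | not collected | none | yes | not applicable |
| 10.6.1 | example of a provider's record | not mentioned | yes | not applicable |

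Five things follow.

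1. **Recorder bias is named and not addressed.** No section provides for self-marking or for a masked or independent recorder. Section 19 shows the VSQ, FSFI, VSI and PGI-I forms but no VAS form. The sample data sheet at 19d is not reproduced in the text available, so its content is unknown.
2. **Self-marking is feasible on the protocol's own terms.** The same women already complete three forms at visit 1 and four at visit 2.
3. **Exposure is limited to week 12.** The baseline VAS is listed before randomization, so knowledge of the arm cannot influence it.
4. **Mode still matters at baseline.** The endpoint is a change score. If only the week 12 reading became self-marked, the change would mix a provider's record with a self-rating.
5. **Week 12 timing already suits the VAS.** In 7.2.4 and the 12-week branch of 7.2.5 it is listed ahead of the exam and the discussion of change. The change needed is in who marks the scale.

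The schedule of events in section 20 does not help. It lists the VAS under study team procedures, but the self-completed questionnaires stand under the same heading.

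**The case against.** The strongest reply is that to record need not mean to score. The same lists have staff record adverse events as the participant reports them, and record adherence, which 10.4.4 says rests solely on self-report. Section 10.4.2 describes the VAS as a visual scale. A provider may simply be copying down a mark the woman made. This stands in part: a reader might infer that providers score the scale themselves, and the documents do not establish that. They do establish that 10.6.1 treats the VAS as a provider's record open to bias, and that no section says who makes the mark.

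Other stronger readings also fail.

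- **That all forms should move ahead of the exam.** For the week 12 VAS this is already the listed order. At baseline it would put the forms before GSM diagnosis and the eligibility check, so women later found ineligible would complete them.
- **That 7.2.5 should have the VAS completed alongside the VSQ, FSFI and VSI.** That would add two instruments that the section does not list.
- **That the distortion can be sized.** The documents give neither a VAS standard deviation nor any estimate of recorder influence, so any shift in points would be pure assumption.
- **That self-marking would unbias the VAS.** The women stay unmasked, and 10.6.1 names their reporting bias separately.

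It is also fair to say that little hangs on this. The primary VSQ is self-completed, its items and those of the VSI overlap the three VAS symptoms, 10.1 says formal comparison is not the focus, and the limitation is openly disclosed.

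**Conclusion.** The point holds in a narrow form and is minor. The protocol identifies recorder bias in the VAS, defers it, and leaves unstated a simple step that would remove it. The effect is confined to the recorder's share of bias in three secondary VAS measures at week 12. That share is unknown and may be nil if staff only transcribe. The conclusion does not depend on which reading of the verb is right. If providers score the scale, the procedure should change; if they transcribe, the protocol should say so and 10.6.1 should stop describing the VAS as a measurement exposed to the recorder. It assumes only that women able to complete the VSQ can also mark three scales.

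**What to change.** In 7.2.3, 7.2.4 and the 12-week branch of 7.2.5, replace the VAS instruction with wording such as: *The participant marks the dyspareunia, itching and dryness VAS herself on the VAS form; staff transcribe the marks and do not score the scales.* Attach the form in section 19. Use the same mode at baseline and week 12 so that the change score compares like with like. Keep the existing week 12 order, leave the baseline order alone, and add no instruments to 7.2.5.

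In 10.6.1, state that recorder bias in the VAS is limited in this way and that patient-report bias from open treatment remains.

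The cost is negligible: a printed form, wording changes, and the IRB review that 13.2 requires for amendments and participant materials. No visits or staff are added. If enrollment has already begun, the amendment should say from which participant the new mode applies, so that no woman's change score spans two modes unnoticed.

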13.1 Ethical Standard

The investigator will ensure that this study is conducted in full conformity with Regulations for the Protection of Human Subjects of Research codified in 45 CFR Part 46, 21 CFR Part 50, 21 CFR Part 56, and/or the ICH E6.

13.2 Institutional Review Board

The protocol, informed consent form(s), recruitment materials, and all participant materials will be submitted to the IRB for review and approval. Approval of both the protocol and the consent form must be obtained before any participant is enrolled. Any amendment to the protocol will require review and approval by the IRB before the changes are implemented to the study. All changes to the consent form will be IRB approved; a determination will be made regarding whether previously consented participants need to be re-consented.

13.3 Informed Consent Process

13.3.1 Consent/Accent and Other Informational Documents Provided to Participants

Consent forms describing in detail the study agent, study procedures, and risks are given to the participant and written documentation of informed consent is required prior to starting intervention/administering study product. The following consent materials are submitted with this protocol: patient consent form, key study information.

13.3.2 Consent Procedures and Documentation

Informed consent is a process that is initiated prior to the individual's agreeing to participate in the study and continues throughout the individual's study participation. Extensive discussion of risks and possible benefits of participation will be provided to the participants and their families. Consent forms will be IRB-approved and the participant will be asked to read and review the document. The investigator will explain the research study to the participant and answer any questions that may arise. All participants will receive a verbal explanation in terms suited to their comprehension of the purposes, procedures, and potential risks of the study and of their rights as research participants. Participants will have the opportunity to carefully review the written consent form and ask questions prior to signing. The participants should have the opportunity to discuss the study with their surrogates or think about it prior to agreeing to participate. The participant will sign the informed consent document prior to any procedures being done specifically for the study. The participants may withdraw consent at any time throughout the course of the trial. A copy of the signed informed consent document will be given to the participants for their records. The rights and welfare of the participants will be protected by emphasizing to them that the quality of their medical care will not be adversely affected if they decline to participate in this study.

A copy of the signed informed consent document will be stored in the subject's research record. The consent process, including the name of the individual obtaining consent, will be thoroughly documented in the subject's research record. Any alteration to the standard consent process (e.g. use of a translator, consent from a legally authorized representative, consent document presented orally, etc.) and the justification for such alteration will likewise be documented.

CONFIDENTIAL

This material is the property of the NYU School of Medicine and Langone Medical Center. Do not disclose or use except as authorized in writing by the study sponsor
Interventional Template Version: 11 January 2019

13.4 Posting of Clinical Trial Consent Form

N/A

13.5 Participant and Data Confidentiality

Information about study subjects will be kept confidential and managed according to the requirements of the Health Insurance Portability and Accountability Act of 1996 (HIPAA). Those regulations require a signed subject authorization informing the subject of the following:

- What protected health information (PHI) will be collected from subjects in this study
- Who will have access to that information and why
- Who will use or disclose that information
- The rights of a research subject to revoke their authorization for use of their PHI.

In the event that a subject revokes authorization to collect or use PHI, the investigator, by regulation, retains the ability to use all information collected prior to the revocation of subject authorization. For subjects that have revoked authorization to collect or use PHI, attempts should be made to obtain permission to collect at least vital status (i.e. that the subject is alive) at the end of their scheduled study period.

Participant confidentiality is strictly held in trust by the participating investigators, their staff, and the sponsor(s) and their agents. This confidentiality is extended to cover testing of biological samples and genetic tests in addition to the clinical information relating to participants.

Therefore, the study protocol, documentation, data, and all other information generated will be held in strict confidence. No information concerning the study or the data will be released to any unauthorized third party without prior written approval of the sponsor.

The study monitor, other authorized representatives of the sponsor, representatives of the IRB or pharmaceutical company supplying study product may inspect all documents and records required to be maintained by the investigator, including but not limited to, medical records (office, clinic, or hospital) and pharmacy records for the participants in this study. The clinical study site will permit access to such records.

The study participant's contact information will be securely stored at each clinical site for internal use during the study. At the end of the study, all records will continue to be kept in a secure location for as long a period as dictated by local IRB and Institutional regulations.

Study participant research data, which is for purposes of statistical analysis and scientific reporting, will be transmitted to and stored at NYU Langone Medical Center. This will not include the participant's contact or identifying information. Rather, individual participants and their research data will be identified by a unique study identification number. The study data entry and study management systems used by clinical sites and by NYU Langone Medical Center research staff will be secured and password protected. At the end of the study, all study databases will be de-identified and archived at the NYU Langone Medical Center.

13.5.1 Research Use of Stored Human Samples, Specimens, or Data

- Intended Use: Samples and data collected under this protocol may be used to study GSM. No genetic testing will be performed.

CONFIDENTIAL

This material is the property of the NYU School of Medicine and Langone Medical Center. Do not disclose or use except as authorized in writing by the study sponsor
Interventional Template Version: 11 January 2019

- Storage: Access to stored samples will be limited using locked cabinets. Samples and data will be stored using codes assigned by the investigators. Data will be kept in password-protected computers. Only investigators will have access to the samples and data.
- Tracking: Data will be tracked using Trialmaster.

Data collected for this study will be analyzed and stored using TrialMaster. After the study is completed, the de-identified, archived data will be transmitted to and stored on the NYUMC computer network, under the supervision of [name], for use by other researchers including those outside of the study without patient identifiers. Permission to transmit data to NYUMC computer network will be included in the informed consent.

There will be no biological samples stored.

When the study is completed, access to study data will be provided through the password protected NYUMC computer network.

14 Data Handling and Record Keeping

14.1 Data Collection and Management Responsibilities

Data collection is the responsibility of the clinical trial staff at the site under the supervision of the site PI. The investigator is responsible for ensuring the accuracy, completeness, legibility, and timeliness of the data reported.

All source documents should be completed in a neat, legible manner to ensure accurate interpretation of data. Black ink is required to ensure clarity of reproduced copies. When making changes or corrections, cross out the original entry with a single line, and initial and date the change. DO NOT ERASE, OVERWRITE, OR USE CORRECTION FLUID OR TAPE ON THE ORIGINAL.

Copies of the electronic CRF (eCRF) will be provided for use as source documents and maintained for recording data for each participant enrolled in the study. Data reported in the eCRF derived from source documents should be consistent with the source documents or the discrepancies should be explained and captured in a progress note and maintained in the participant's official electronic study record.

Clinical data (including AEs, concomitant medications, and expected adverse reactions data) and clinical laboratory data will be entered into TrialMaster. The data system includes password protection and internal quality checks, such as automatic range checks, to identify data that appear inconsistent, incomplete, or inaccurate. Clinical data will be entered directly from the source documents.

